2.1.1.4 Baseline

2.1.1.4.1 Baseline for efficacy analyses

The baseline eDiary score corresponding to a score in the 7 days prior to the first dosing visit assessment, the baseline will be defined as the baseline week (see Table 2-1).

For DLQI/CDLQI [REDACTED], baseline is the assessment obtained at Visit 201. For a subject who receives partial dose for the first dose day of study treatment, the baseline will be still defined according to the first dosing date of the partial dose. For a subject without any administration of study dose, the baseline assessment will be his last assessment in the Extension study. If a questionnaire was completed more than once on the same date, on the last date on or before treatment start date, then the worst outcome of the duplicate observations on that date will be used as baseline.

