2.3.2 Disease characteristics at baseline (baseline is defined in Section 2.1.1.4)

- CU Index category
- [REDACTED]
- Baseline UAS7 score
- Duration of CSU – collected at Visit 201
- Baseline AAS7 score
- Baseline proportion of AAS7 = 0
- Type of prior urticaria medication – collected at Visit 201

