5.5.2.2 Secondary analysis for binary endpoints

For binary endpoints of UAS7=0/DLQI 0-1 at Week 12, the secondary analysis will be performed based on the data after the missing data imputation for the intercurrent events has been performed.

The SAS procedure `proc mi` will be used for multiple imputation with the following sample code:

```
proc mi data=... out=... nimpute=... seed=123;  
by group;cuin  
class ige cuind group week12;  
fcs logistic (week12 = ige cuind group baseline / details);  
var ige cuind group baseline week12;  
run;  
where group = treatment group  
    ige = baseline IgE
```

cuind = baseline CU index
baseline = baseline UAS7 score
week12 = binary response of UAS7=0/DLQI 0-1 at Week 12 in TRT1.

If the imputation model does not converge, remove the covariates as needed until it converges.

The SAS procedure `proc freq`, and `proc mianalyze` will be used for the analysis. Sample code refer to Section 5.5.1. Wilson score method is not necessary for 95% confidence limits calculation in secondary analysis. Other methods could be performed as needed.

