5.5.2.3 Secondary analysis for count endpoint

For count endpoint of cumulative weeks with AAS7=0 up to Week 12, the secondary analysis will be performed based on the data after the missing data imputation for the intercurrent events have been performed.

The SAS procedure `proc mi` will be used for multiple imputation with the following sample code:

```
proc mi data=... out=... nimpute=... seed=123;  
by group;cuin  
class ige cuind group week1-week12;  
fcs logistic (week1-week12 = ige cuind group baseline / details);  
var ige cuind group baseline week1-week12;  
run;
```

where group = treatment group
ige = baseline IgE
cuind = baseline CU index
baseline = baseline UAS7 score
week1-week12 = binary response of AAS7=0 at Week 1-12 in TRT1.

If the imputation model does not converge, remove the covariates as needed until it converges.

The SAS procedure `proc genmod` will be used to calculate the group means for each imputed dataset with the following sample code:

```
ods output LSMeans = sumstat;  
proc genmode data = ... order = internal;  
by _imputation_;  
class group / param = glm;  
model cum = group / noint dist = negbin link = log;  
lsmeans group / cl ilink e;  
run;
```

where _imputation_ = the index for imputation times
group = treatment group
cum = the cumulative weeks of AAS7=0 up to week 12
sumstat is the dataset which includes the mean estimate and the standard error in each group.

The SAS procedure `proc mianalyze` will be used to combine the parameter estimates across imputed datasets with the following sample code:

```
ods output ParameterEstimates = pe_comb;
proc mianalyze data = sumstat;
by group;
ModelEffects Mu;
stderr StdErrMu;
run;
```

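### The imputation models for DLQI 0-1 and weekly AAS7 = 0 leave out each endpoint's own baseline and earlier observed values, which are collected and are likely its strongest predictors

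*SAP*

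**What the plan says.** For DLQI 0-1, SAP 5.5.2.2 specifies "fcs logistic (week12 = ige cuind group baseline / details" with the variable list "var ige cuind group baseline week12". The target is "week12 = binary response of UAS7=0/DLQI 0-1 at Week 12 in TRT1", so UAS7 = 0 and DLQI 0-1 share one block. The term called baseline is defined there as "baseline = baseline UAS7 score".

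For the cumulative number of angioedema-free weeks, SAP 5.5.2.3 specifies "fcs logistic (week1-week12 = ige cuind group baseline / details" with the variable list "var ige cuind group baseline week1-week12". Baseline is again defined as baseline UAS7.

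Both blocks run separately by group, so group is constant within each fit. IgE, CU index and baseline UAS7 are the only working predictors.

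The plan holds more than this. For DLQI, "baseline is the assessment obtained at Visit 201" (SAP 2.1.1.4.1), and Protocol Table 8-1 also schedules it at Weeks 4, 8 and 12. SAP 2.3.2 lists "Baseline AAS7 score" and the baseline share with AAS7 = 0. AAS is recorded every evening in the diary (Protocol 8.3.1.2).

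The SAP text adds no DLQI or AAS7 predictor. Section 2.6.1 refers both endpoints back to the primary rules, and its DLQI paragraph says that the imputation rests on the UAS7 = 0 proportion.

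**The concern.** SAP 2.5.3 describes multiple imputation as conditioning on the observed data. As coded, two subjects in the same group with equal IgE, CU index and baseline UAS7 get the same imputation probability for a missing AAS7 week, even if one has been free of angioedema throughout and the other has had it every week. The same holds for DLQI 0-1 at Week 12, whatever the subject's DLQI was at baseline and Week 8.

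Missing at random is therefore assumed given three baseline variables, none from the instrument being imputed. At stake are the credibility of that assumption, some precision, and the shape of the AAS7 count distribution, for which SAP 2.6.1 plans a cumulative frequency plot.

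**Working it through.** The plan attaches no figure to this point, so there is none to reproduce.

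**1. Models against data**

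| Endpoint | Working predictors | Own-instrument data held | In the model? |
|---|---|---|---|
| DLQI 0-1, Week 12 | IgE, CU index, baseline UAS7 | Baseline, Weeks 4 and 8 | No |
| AAS7 = 0, Weeks 1-12 | IgE, CU index, baseline UAS7 | Baseline AAS7, daily diary | No |

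Weeks 1 to 12 do appear in the AAS7 variable list. The equation, however, names its effects explicitly, and no week is among them.

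**2. Where multiple imputation applies.** Under SAP 2.5.3 it covers data missing because of study termination. Step 1 of that section also lists intermittent gaps, although another sentence there sends all other missing scores to non-response. The number of subjects affected is not stated.

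**3. Two-class illustration (assumed).** Let 80% of subjects always have AAS7 = 0 and 20% never. A model without history gives everyone a probability of 0.8. Over missing Weeks 9 to 12:

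- Always-free subjects: true 4 weeks, imputed 4 × 0.8 = 3.2, error −0.8.
- Never-free subjects: true 0, imputed 3.2, error +3.2.
- Group mean error if missingness is unrelated to class: 0.8 × (−0.8) + 0.2 × 3.2 = 0.
- Between-subject SD of the four-week count among imputed subjects: true 4 × √(0.8 × 0.2) = 1.6; imputed √(4 × 0.8 × 0.2) = 0.8.

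The mean is preserved and the spread is halved. If the always-free share is q among subjects with data and p among those without, the mean error per imputed subject is 4(q − p) weeks. It is non-zero only when missingness is related to class.

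**4. Simulation (illustrative).** There are 250 subjects per group, the smallest scenario in SAP Table 3-1. Everything else is assumed:

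- Latent within-subject correlation 0.3, 0.5 or 0.7; correlation of 0.2 in size between baseline UAS7 and the subject effect; 5% or 20% of subjects missing.
- DLQI 0-1 rate 50%. AAS7 missing from Week 5, with a weekly AAS7 = 0 rate of about 69%.
- Missingness either completely random or more frequent after poor earlier response.
- IgE and CU index left out of both models. The own-history model adds latent baseline, Week 4 and Week 8 values for DLQI, and baseline status plus the proportion of prior weeks free for AAS7.
- 300 replicates with 10 imputations (DLQI); 60 replicates with 5 (AAS7).

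Each cell gives the range over the three correlations. Bias is the mean difference from the complete-data estimate, and SD is the SD of that difference.

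| Endpoint, missingness | Missing | Bias, SAP model | Bias, own history | SD, SAP model | SD, own history |
|---|---|---|---|---|---|
| DLQI (points), random | 5% | −0.02 to +0.04 | −0.03 to +0.02 | 0.79–0.83 | 0.64–0.76 |
| DLQI (points), random | 20% | +0.02 to +0.12 | −0.04 to +0.13 | 1.52–1.69 | 1.30–1.53 |
| DLQI (points), response-related | 5% | +0.24 to +0.69 | −0.04 to +0.06 | 0.75–0.78 | 0.59–0.77 |
| DLQI (points), response-related | 20% | +1.51 to +3.63 | +0.04 to +0.09 | 1.64–1.74 | 1.23–1.64 |
| AAS7 (weeks), random | 20% | −0.011 to +0.011 | +0.001 to +0.006 | 0.067–0.086 | 0.050–0.059 |
| AAS7 (weeks), response-related | 5% | +0.006 to +0.035 | −0.005 to −0.004 | 0.022–0.039 | 0.022–0.026 |
| AAS7 (weeks), response-related | 20% | +0.058 to +0.189 | −0.020 to +0.004 | 0.048–0.085 | 0.047–0.051 |

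Between-subject SD of the AAS7 count with 20% missing, SAP model against complete data:

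- Random: 2.58 vs 2.76, 3.16 vs 3.40, 3.72 vs 4.04, a shrinkage of 6.5%, 7.1% and 7.9%.
- Response-related: 2.61 vs 2.80, 3.08 vs 3.36, 3.61 vs 4.01, a shrinkage of 6.8%, 8.3% and 10.0%.

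With 5% missing the shrinkage is about 1 to 2%. The own-history model keeps the spread within 0.02 weeks of complete data throughout.

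**The case against.** The strongest reply is that the missingness is administrative. The end of SAP Section 1 describes a sponsor decision communicated on one date and not prompted by safety. Subjects who stop for adverse events, lack of efficacy or other reasons are handled by retrieved data or non-response. Nothing in the documents ties termination before Week 12 to a subject's earlier DLQI or AAS7. This stands. A reader might infer that the planned results are biased, but the documents do not support that; the larger figures above need response-related missingness, which is assumed.

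A reader might also infer from the two-class example that one imputed value in five for an always-free subject is wrong, and that the estimate is off to match. The individual error is real under that assumption, but it cancels in the group mean, which is what 5.5.2.3 estimates.

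Nor do the documents show that own-instrument history is the best predictor, because they give no correlations. It is likely the strongest; that is a judgement.

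Two other replies carry less weight. The blocks are sample code, but nothing else in the SAP names predictors for these endpoints. A short covariate list is consistent with 2.5.3, but there baseline UAS7 is the endpoint's own baseline; for DLQI and AAS7 it is not.

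One practical caution stands: entering every prior week as a separate term in per-arm logistic models invites separation, and the SAP's non-convergence rule could then remove the added terms.

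**Conclusion.** The omission is plain in both code blocks, and the data to repair it are already collected. Under completely random missingness, the group means are essentially unbiased; the cost is some lost precision (in the illustration, DLQI error SD 1.5–1.7 against 1.3–1.5 points at 20% missing) and an understated spread of the AAS7 week count. Upward bias appears in the illustration only when poor earlier responders are missing more often.

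The actual size cannot be computed, because the number of subjects imputed is not given. SAP 2.6.2 confines these secondary endpoints to descriptive summaries, so no test result depends on them. This is a worthwhile improvement, not a threat to the trial's conclusions.

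**What to change.** - **SAP 5.5.2.2:** give DLQI 0-1 its own imputation call. Add baseline DLQI total, and Week 4 and Week 8 DLQI where observed.
- **SAP 5.5.2.3:** add baseline AAS7 = 0 (yes/no) and a compact summary of observed AAS7 history, either previous-week status or the proportion of prior weeks free, to limit separation.
- **Both:** keep baseline UAS7 as an additional covariate, and state that own-history terms are the last to be dropped if a model does not converge.
- **SAP 2.6.1:** align the DLQI sentence that bases imputation on UAS7 = 0 with the revised model.

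If the final outputs already exist, report the extended models as a sensitivity analysis. No new data are needed; the cost is minor programming and some convergence risk.

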5.5.2.3 Secondary analysis for count endpoint

For count endpoint of cumulative weeks with AAS7=0 up to Week 12, the secondary analysis will be performed based on the data after the missing data imputation for the intercurrent events have been performed.

The SAS procedure `proc mi` will be used for multiple imputation with the following sample code:

```
proc mi data=... out=... nimpute=... seed=123;  
by group;cuin  
class ige cuind group week1-week12;  
fcs logistic (week1-week12 = ige cuind group baseline / details);  
var ige cuind group baseline week1-week12;  
run;
```

where group = treatment group
ige = baseline IgE
cuind = baseline CU index
baseline = baseline UAS7 score
week1-week12 = binary response of AAS7=0 at Week 1-12 in TRT1.

If the imputation model does not converge, remove the covariates as needed until it converges.

The SAS procedure `proc genmod` will be used to calculate the group means for each imputed dataset with the following sample code:

```
ods output LSMeans = sumstat;  
proc genmode data = ... order = internal;  
by _imputation_;  
class group / param = glm;  
model cum = group / noint dist = negbin link = log;  
lsmeans group / cl ilink e;  
run;
```

where _imputation_ = the index for imputation times
group = treatment group
cum = the cumulative weeks of AAS7=0 up to week 12
sumstat is the dataset which includes the mean estimate and the standard error in each group.

The SAS procedure `proc mianalyze` will be used to combine the parameter estimates across imputed datasets with the following sample code:

```
ods output ParameterEstimates = pe_comb;
proc mianalyze data = sumstat;
by group;
ModelEffects Mu;
stderr StdErrMu;
run;
```

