1.2 Study objectives and endpoints

[figure not shown]
Table 1-1 Objectives and related endpoints

[figure not shown]
Objective(s)	Endpoint(s)
Primary objective(s)	Endpoint(s) for primary objective(s)

 To evaluate the efficacy of retreatment with ligelizumab 72 mg or 120 mg q4w in subjects previously treated in the core studies (CQGE031C2302/CQGE031C2303) To evaluate the efficacy of retreatment with ligelizumab in the subgroup of these subjects who achieved a weekly urticaria activity score (UAS7) ≤ 6 after 12 weeks of treatment in these core studies 	
 The proportion of subjects with well-controlled disease (UAS7 ≤ 6) at Week 12
Secondary objective(s)	Endpoint(s) for secondary objective(s)
For retreatment efficacy evaluation:	

 To describe the efficacy of ligelizumab 72 mg or 120 mg q4w in achieving complete control of chronic spontaneous urticaria (CSU) at Week 12 when used as retreatment for subjects previously treated in the core studies (CQGE031C2302/CQGE031C2303) To describe the efficacy of ligelizumab with respect to a reduction from extension study baseline in the UAS7 and its components (weekly itch severity score (ISS7) and weekly hives severity score (HSS7) at Week 12 in all subjects receiving the same dose regimen as in the core studies, i.e. 72 mg or 120 mg q4w To describe the efficacy of ligelizumab in achieving an angioedema-free period at Week 12 in all subjects receiving the same dose regimen as in the core studies, i.e. 72 mg or 120 mg q4w 	
 The proportion of subjects with completely controlled disease (UAS7 = 0) at Week 12 Absolute change from extension study baseline in the UAS7 and its components (ISS7 and HSS7) at Week 12 Cumulative number of weeks that subjects achieve weekly angioedema activity score (AAS7) = 0 between extension study baseline and Week 12

Objective(s)	Endpoint(s)

To describe the efficacy of ligelizumab in achieving Dermatology Life Quality Index (DLQI) = 0-1 at Week 12 when used as re-treatment for all subjects receiving the same dose regimen as in the core studies, i.e. 72 mg or 120 mg q4w	
Percentage of subjects achieving DLQI = 0-1 at Week 12
For self-administration efficacy evaluation:	

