The absolute change from extension study baseline in UAS7 score at Week 12 will be summarized descriptively, it will be provided together with 95% confidence interval. The change from extension study in UAS7 components (ISS7 and HSS7) will also be provided in descriptive manner at Week 12.

Similar missing data imputation rules as the primary endpoint analysis based on change from baseline in UAS7 score at week 12 will be used for this secondary endpoint analyses. The imputations for ISS7 and HSS7 will follow the same missing data imputation rules.

- Percentage of subjects achieving DLQI = 0-1 (no impact on subjects QoL) at Week 12 after retreatment of ligelizumab for subjects receiving the same dose regimen as in the core studies.

An overall score will be calculated according to the scoring manual. The proportion of subjects with overall DLQI scores ≤ 1 at Week 12 will be summarized in a descriptive manner, it will be provided together with a 95% Clopper-Pearson exact confidence interval. Similar missing data imputation rules as the primary endpoint analysis will be applied in this secondary efficacy endpoint analysis. The missing data imputation will be based on the proportion of subject with UAS7 = 0 at week 12.

- Cumulative number of weeks that subjects achieve AAS7 = 0 between extension study baseline and Week 12

The cumulative number of weeks achieving AAS7 = 0 response between baseline and Week 12 will be derived based on the AAS eDiary. A weekly AAS7 score will be derived by adding up the daily scores of the 7 days preceding the visit, and ranges from 0 to 105. For a weekly AAS7 score, if one or more of the daily scores are missing, the same principles as handling the weekly score from UPDD will be applied to handle the missing data. If the AAS7 score is missing, similar missing imputation rules as the primary analysis will be applied on AAS7 = 0 proportion over the first 12 weeks. The imputed AAS7 = 0 will be used for the cumulative number of weeks that subjects achieve AAS7 = 0 response calculation. The cumulative frequency plot will be provided together with the summary statistics.

- Percentage of subjects achieving UAS7 ≤ 6 (well-controlled urticaria) at 12 weeks after starting self-administration in the first half of the treatment period.

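### The negative binomial standard error for cumulative weeks with AAS7 = 0 ignores the 12-week bound and will usually be too large; the group means are unaffected

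*SAP*

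**What the plan says.** SAP 1.2 defines the endpoint as "Cumulative number of weeks that subjects achieve weekly angioedema activity score (AAS7) = 0 between extension study baseline and Week 12", and SAP 2.6.1 repeats it. For reporting, 2.6.1 commits only to this: "The cumulative frequency plot will be provided together with the summary statistics". Section 2.6.2 says the secondary analyses are descriptive.

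The model appears only in the appendix sample code, SAP 5.5.2.3. The imputed quantities are "week1-week12 = binary response of AAS7=0 at Week 1-12 in TRT1", and the analysed variable is "cum = the cumulative weeks of AAS7=0 up to week 12". PROC GENMOD "will be used to calculate the group means for each imputed dataset with the following sample code", with the statement "model cum = group / noint dist = negbin link = log". It runs by imputation with group as a class effect, so the arms share one dispersion parameter. Neither a robust nor an empirical variance is requested. PROC MIANALYZE then takes the mean on the week scale with "stderr StdErrMu".

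**The concern.** A sum of twelve yes/no indicators cannot exceed 12. A negative binomial variable has no ceiling, and its variance is at least its mean. With one free mean per arm, the fitted mean equals the sample mean, so the only thing the model adds is the standard error, and that is the part the bound makes unreliable. Data less variable than Poisson push the dispersion to zero and leave a Poisson variance that is too large. A cluster at 0 together with a cluster at 12 inflates the dispersion. A cluster at 0 is possible because the missing-week rules follow the primary analysis, which includes non-responder imputation.

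What is at stake is the width of any pooled interval around each arm's mean. Because the dispersion is shared, the shape of one arm also affects the standard error of the other.

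**Working it through.** **Inputs.** Range 0 to 12 and model: SAP 5.5.2.3. Sample size: 250 per group less 10% dropout = 225, the smallest scenario in SAP Table 3-1; it scales the standard errors but cancels from their ratios. The documents state no mean, SD or standard error for this endpoint, so there is no figure to reproduce, and every distribution below is an assumption.

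**Formulas.** With mean μ and dispersion k, the model-based standard error of the mean is √[(μ + kμ²)/n]. The true one is √(σ²/n).

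**Bound that needs no shape.** A variable on 0 to 12 has variance of at most μ(12 − μ). The model variance is at least μ if k ≥ 0. When μ > 11, 12 − μ < 1, so μ(12 − μ) < μ and the model variance must exceed the true variance.

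**Refits.** k was fitted by maximum likelihood with k ≥ 0, n = 225. Where some subjects are in neither cluster, they are spread evenly over the range shown.

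| Assumed shape | Mean | σ² | k | Model SE | True SE | Ratio | Extra 95% half-width (weeks) |
|---|---|---|---|---|---|---|---|
| 70% at 12, rest over 1–11 | 10.2 | 10.56 | 0.006 | 0.219 | 0.217 | 1.01 | 0.01 |
| 75% at 12, 5% at 0, rest over 1–11 | 10.2 | 13.16 | 0.063 | 0.273 | 0.242 | 1.13 | 0.06 |
| 70% at 12, 10% at 0, rest over 1–11 | 9.6 | 17.84 | 0.234 | 0.372 | 0.282 | 1.32 | 0.18 |
| 90% at 12, rest over 1–11 | 11.4 | 4.24 | 0 | 0.225 | 0.137 | 1.64 | 0.17 |
| 80% at 12, 20% at 0 | 9.6 | 23.04 | 0.572 | 0.526 | 0.320 | 1.65 | 0.41 |
| 80% at 12, rest over 6–11 | 11.3 | 2.54 | 0 | 0.224 | 0.106 | 2.11 | 0.23 |

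Example, last row: μ = 0.8×12 + 0.2×8.5 = 11.3. The model gives √(11.3/225) = 0.224 and the truth is √(2.54/225) = 0.106. The 95% intervals are 10.9 to 11.7 and 11.1 to 11.5. For 80% at 12 and 20% at 0 they are 8.6 to 10.6 and 9.0 to 10.2.

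**Wider set.** Over 16 assumed distributions (13% to 90% at 12, 0% to 15% at 0) the ratio ran from 1.01 to 2.89. It was at least 1.07 in 14 of them and never below 1. In 3,000 random shapes with added mass at 12, the median ratio was 1.15 and fewer than 2% fell below 1. The fitted model put 17% to 38% of its probability above 12 weeks, which cannot occur.

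**Coverage.** In simulations of two arms of 225 (400 replicates, four shapes), the nominal 95% interval covered 95% to 100% of the time with the negative binomial standard error, and 93% to 95% with SD/√n.

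**Effect after pooling.** The ratios apply to the within-imputation variance U. Rubin's total is U + (1 + 1/m)B, where m is the number of imputations. B depends only on the means and is unchanged, so the pooled interval is inflated by no more than these ratios, and by less where B is sizeable.

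**The case against.** The strongest reply concerns weight. The documents nowhere show the distribution of AAS7 = 0 weeks; SAP 2.3.2 only plans a baseline summary. A reader might infer that the counts are known to pile up at 12, or that the standard error is wrong by a large factor. The documents support neither: the pile-up is plausible but assumed, and for some shapes the standard error is right to within 1% or 2%.

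A reader might also infer that a promised confidence interval for a key secondary endpoint is invalid. SAP 2.6.1 promises no interval here, although it does for the other secondary efficacy endpoints, and key secondary is the SAP's heading for all of these endpoints; the protocol calls them secondary. The sample code does request confidence limits and pools a standard error, so an interval would be produced, but only through the appendix. The promised cumulative frequency plot would show any ceiling directly.

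The error is also almost always conservative, and small on the week scale. Finally, the collapse to Poisson assumes that the software keeps k ≥ 0, which was not tested in PROC GENMOD; the largest ratios come from that branch.

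All of this stands, and it limits severity. It does not justify the model: the code's stated purpose is a group mean, which needs no distributional model.

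**Conclusion.** Wrong as written, minor severity. The group means are correct, but their standard errors come from a variance that does not fit a 0-to-12 count. With k ≥ 0 the standard error is necessarily too large for a group mean above 11 weeks. Otherwise it is about 1.0 to 2.1 times the true value in the shapes tabulated and up to 2.9 in the wider set, nearly always on the wide side. These sizes rest on assumed distributions and a maximum-likelihood fit with k ≥ 0; the absolute widths also rest on 225 per arm.

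It would be tempting to conclude that the endpoint's result is biased or that an efficacy claim is at risk. Neither follows: the means do not move, no between-arm test, alpha or margin depends on this endpoint, and the usual error understates precision.

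**What to change.** In SAP 5.5.2.3, replace the PROC GENMOD step. For each imputed dataset and arm, run PROC MEANS on the cumulative weeks with mean= and stderr=, and pass those two quantities to PROC MIANALYZE. Do not copy the output statement in SAP 5.5.2.1 unchanged: it requests std=, the standard deviation, and labels it a standard error. Keep the cumulative frequency plot. State in SAP 2.6.1 that the arm means are pooled with the ordinary standard error of the mean, and whether a 95% interval will be reported.

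The cost is a short SAP edit and simpler code. It needs no new data, does not change the point estimates, and removes the dispersion shared between arms.
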